**Fig. 7. Study Phases: Baseline & Randomization** includes 2 Sound Sweeps tests: Test 1 with PBO and  $\approx$  5-7 days later Test 2 with either AMPH or PBO. **Treatment Phase** includes 30 TCT sessions with outcome measures after 10, 20 and 30 sessions. **Post-treatment** tests assess both immediate biomarker changes and 12-week durability of outcome gains.

**Assessments:** 30 sessions of TCT will be completed, based on our findings (Fig. 4) and evidence that TCT efficacy is dose-dependent. Assessment dates could be based on either: 1. session # (10, 20 and 30 and 12 weeks later); or 2. Time (days) since starting TCT. In our experience TCT rates closely match 3/week (30 sessions mean = 65 days; 90% of subjects completed their 30 TCT sessions within 11 weeks. Primary analyses will be based on session #, but session dates are recorded and confirmatory analyses will define assessment points based on time passage. Candidate predictive biomarkers are re-tested after session 30.

**General Clinical Monitoring:** In addition to their established ongoing care, patients are carefully monitored at each session as per our well-established procedures, and through to the week-22 follow-up, for any clinical changes. Each week, a member of our research staff checks vital signs and weight, does a detailed assessment of symptom changes, focusing on psychosis, depression, suicidality and abnormal movements, and tests UTox and pregnancy. A designated unblinded staff member processes UTox results in the event that a PBO-arm subject tests positive for amphetamine; any clinical worsening or UTox positive for recreational drugs (other than AMPH in AMPH-arm subjects) or a positive pregnancy test is promptly reviewed with the on-site Psychiatrist; any “yes” on the Columbia Suicide Severity Rating Scale (C-SSRS) “Since Last Visit”, or an exacerbation of psychotic symptoms, prompts detailed review, with appropriate clinical interventions. Patients testing positive for recreational drugs will be retested in 1 week; patients with 3 positive tests no longer continue in the study. **Data from subjects who, for this or other reasons, do not complete the full study are carried forward in an “intent to treat” design, and their data are analyzed using linear mixed models.**

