A “Go” decision requires: 1) confirmation of target engagement (APS learning, AMPH>PBO,  $p < 0.05$ ); 2) evidence of gains from PACT ( $d \geq 0.5$  (AMPH > PBO)) in primary clinical, neurocognitive and/or functional measures (Fig. 8), and 3) the absence of adverse effects of AMPH that are significantly greater than PBO levels. The decision to not use traditional statistical significance as “Go” criteria for Aim 2 reflects this RFA’s call for “Pilot” studies, the need to identify candidate treatments for a subsequent larger “n” Confirmatory Efficacy R01 study, and the limits in sample size resulting from the 3-year R33 duration. Cohen defined a medium effect size ( $d=0.5$ ) as one that is “visible to the naked eye,” and this amount of change is viewed as clinically meaningful in trials targeting negative symptoms. This  $d=0.5$  “Go” threshold for Aim 2 corresponds to a “number needed to treat” (NNT) value  $\approx 3.62$ . While a “Go” decision does not require identification of a biomarker predicting greater PACT

sensitivity (Aim 3), the identification of one or more meaningful predictors that could be incorporated into a Confirmatory Efficacy trial would favorably impact a “Go” decision.

Staff assessing outcome measures are blind to treatment arm, and for some measures receive training using videotaped and practice interviews until achieving high (ICC>.80) reliability based on 20 assessments by 2 raters. We achieve high inter-rater reliability (e.g., ICC>0.85 for PANSS total), and check for rater drift each 90d.

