**Symptoms** are assessed (Fig. 4B) to track clinical status, and TCT response. TCT reduces both positive and negative symptoms of psychosis, and we predict that AMPH will augment these effects via enhanced TCT learning (i.e. not via a lasting direct pharmacological effect of AMPH), detected by the Positive & Negative Syndrome Scale. For this reason, and based on the need to limit total outcome measures, PANSS Total Score is the primary clinical outcome measure. Positive and negative symptom subscales, as well as PANSS factor-derived measures, will be assessed in exploratory analyses. Other secondary clinical measures will include: 1) Psychotic Symptom Rating Scales (PSRS; assesses auditory hallucinations); 2) Young Mania Rating Scale; 3) Patient Health Questionnaire-9 (PHQ-9; current depressive symptoms); 4) Abnormal Involuntary Movement Scale (AIMS); 5) C-SSRS; “Lifetime/Recent version” at screen; “Since Last Visit” at follow-up visits). The C-SSRS is a reliable, valid and sensitive measure of suicidal ideation; any “yes” in C-SSRS prompts an immediate full evaluation/action plan by a study M.D.; and 7) AMPH Cessation Symptom Assessment (ACSA).

**Neurocognition:** Change in MCCB Composite performance from baseline is one outcome measure. The MCCB measures 7 cognitive domains: SP, A/V, WM (verbal and nonverbal), verbal learning, visual learning, reasoning/problem solving and social cognition. Details are found in; past studies by the PI of drug effects on MCCB performance include. Since the MCCB is assessed multiple times, alternate forms of the HVLT-R and BVMT-R are used in counterbalanced order. MCCB Global Composite T-score (MCCB-C) is the primary neurocognitive outcome measure. Individual MCCB domain T-scores are used in secondary analyses to determine whether an overall effect is driven by specific aspects of neurocognition; TCT effects on verbal learning performance are known to be robust, and should be augmented by AMPH. Baseline and AMPH-enhanced (Test 2 vs. 1) MCCB performance (A/V subscale) will also be tested as potential biomarkers/moderators of AMPH PACT efficacy.

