Indirect indicators of clinical impact included subject attrition, C-SSRS responses, treatment satisfaction and adverse events (AEs). AMPH group subjects were evaluated for abnormal involuntary movements (AIMS) and for deleterious effects of AMPH cessation (AMPH Cessation Symptom Assessment). Analyses included non-parametric (Chi-Square) and parametric (rmANOVA) tests.

Linear mixed-effects models for outcome measures included all subjects who were randomized; df were estimated using the Satterthwaite approximation. Between- and within-group effect sizes for clinical, neurocognitive and functional measures were calculated based on all subjects who completed 30 TCT visits and P30 testing (“completers”). For all analyses, α was set at 0.05; for analyses of the 5 secondary outcome measures, findings were also evaluated with a more restrictive alpha level (0.01) to correct for multiple comparisons.

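### The modified SAP describes AIMS and the amphetamine cessation scale for the AMPH group and specifies no placebo comparison, so neither scale as planned can support the Go safety condition

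*SAP*

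**What the plan says.** **Protocol.** The Symptoms paragraph under Specific Procedures includes "4) Abnormal Involuntary Movement Scale (AIMS" and "7) AMPH Cessation Symptom Assessment (ACSA" in its numbered list of secondary clinical measures. Section 4.3, Outcome Measures, repeats both in the PANSS row. Neither place restricts them to an arm. Under General Clinical Monitoring, a staff member each week "does a detailed assessment of symptom changes, focusing on psychosis, depression, suicidality and abnormal movements", again for all patients.

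The Go decision, set out under Outcome and Go Decisions, has three parts. The third is "the absence of adverse effects of AMPH that are significantly greater than PBO levels". The same section states that "Staff assessing outcome measures are blind to treatment arm". The Design paragraph, the Narrative Study Description (4.2.a) and the SAP's own design section say that neither patients nor staff know the arm.

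**SAP, Project Modification.** The AMPH and memantine studies are combined into three groups with pooled placebo. One sentence reads "Indirect indicators of clinical impact included subject attrition, C-SSRS responses, treatment satisfaction and adverse events (AEs", with no group named. The next reads "AMPH group subjects were evaluated for abnormal involuntary movements (AIMS) and for deleterious effects of AMPH cessation". A closing sentence names Chi-Square tests and repeated-measures ANOVA without saying which groups are compared on which measure.

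**The concern.** A safety condition worded as a comparison with placebo needs placebo values. Everyone in the trial takes an antipsychotic, so abnormal movements, low mood or poor sleep may be present without amphetamine. An AIMS or ACSA score seen in the AMPH group alone cannot be sorted into background and drug effect. The error can run either way: background symptoms may be charged to the drug, or a drug effect may be dismissed as background.

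The protocol itself expects this kind of question. Where it discusses how negative results would guide development, it names psychosis, akathisia and other symptoms as possible adverse effects of AMPH, to be assessed with clinical measures.

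There is a second, conditional stake. A form about stopping amphetamine that goes to one arm tells whoever schedules, gives or completes it what that arm is. PANSS total is scored by a rater and WHODAS by the patient, so both primary outcomes would be exposed.

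**Working it through.** The point rests on no figure in the plan, so the check compares texts.

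**Step 1. Follow each secondary clinical scale from the protocol into the modified SAP.** The protocol's list has six named entries, numbered 1 to 5 and 7.

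| Scale in the protocol list | Place in the modified SAP | Comparison stated |
|---|---|---|
| Psychotic symptom ratings (hallucinations) | Secondary outcome | AMPH vs PBO |
| Young Mania Rating Scale | Secondary outcome | AMPH vs PBO |
| PHQ-9 | Secondary outcome | AMPH vs PBO |
| C-SSRS | Indirect indicator | Test types only, no group limit |
| AIMS | Separate sentence | AMPH group named |
| ACSA | Separate sentence | AMPH group named |

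The modified SAP counts 5 secondary outcomes: PANSS positive and negative (2) plus the first three scales in the table (3), and 2 + 3 = 5. AIMS and ACSA are therefore not among them. They fall outside the mixed models and effect sizes, which are specified for the outcome measures. Two of the six protocol scales end with a single group named and no contrast.

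**Step 2. Read the sentence in context.** The sentence before it names no group. This one opens with the AMPH group as its subject. Elsewhere in the same section, the within-group mixed model and the within-group effect size are each said to cover all groups. Where the authors mean every group, they say so, and the plain reading here is the AMPH group.

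**Step 3. Ask whether the gap depends on that reading.** Suppose both scales were in fact given to every arm. The SAP still states no AMPH-versus-placebo analysis for either. Naming Chi-Square and repeated-measures ANOVA does not supply one, since the latter can be run on change over time within one group. The missing contrast therefore holds on either reading. Only the missing placebo data depends on the plain one.

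**Step 4. Set this against the Go condition.** The condition concerns adverse effects in general and names neither scale. Adverse events and C-SSRS responses are listed without a group limit and can inform it. AIMS and ACSA, as described, cannot. The modification section neither restates nor withdraws the condition.

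**Step 5. Ask whether another measure fills the gap.** The weekly check of abnormal movements covers all patients. However, no rating scale is named for movements there, and the modified SAP does not list that check among what it analyses. It is not clearly a substitute for AIMS, and nothing comparable is described for cessation symptoms.

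**The case against.** The strongest reply is that the SAP never says placebo subjects went without these scales. The section merges two studies and is written in the past tense. The sentence may only separate the AMPH study from the memantine study, or describe what was tabulated after unblinding. The protocol lists both scales for everyone, and if that was followed, placebo data exist and receiving the form reveals nothing. This stands as far as it goes: a reader might infer that there are no placebo observations at all, and the documents do not establish that. It does not supply the missing comparison.

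A reader might also infer that the Go safety condition can no longer be tested. It can: adverse events are sought from all subjects at every visit, C-SSRS responses have no group limit, and PANSS tracks psychosis in every arm. No text says that AIMS or ACSA would capture akathisia. The loss is confined to two scales.

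A reader might further infer that the blind was broken. That would require one-arm use during blinded conduct, which no passage describes.

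Finally, a reader might infer that no cessation assessment falls in the four weeks after the last pill, the follow-up length of the cited lisdexamfetamine discontinuation study. The documents do not support this. They give no ACSA schedule. The last pill is taken an hour before session 30, and the outcome assessment after that session is made off drug, so it follows the last dose. The four weeks belong to the cited study and are not a commitment of this protocol.

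It is also fair to say that no primary efficacy estimate depends on either scale.

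**Conclusion.** The point holds in limited form. Two of the six secondary clinical scales in the protocol, AIMS and ACSA, lose any stated placebo comparison in the modified SAP, and no reason is given. On the plain reading, movement and cessation symptoms are uncontrolled in antipsychotic-treated patients. The Go safety condition remains testable on adverse events and C-SSRS but draws no support from these scales.

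The absence of a specified contrast is a matter of record. That placebo subjects lack the data is an inference from the wording. The threat to blinding is conditional on one-arm administration while the trial was blinded. The memantine protocol is not among the documents, so it is also unknown whether pooled placebo subjects enrolled under it were given either scale. The consequence is for what the trial can say about safety, not for its efficacy estimates.

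**What to change.** Reconcile the modified SAP with the protocol's General Clinical Monitoring, Symptoms, Outcome and Go Decisions, and section 4.3 text. State which arms received AIMS and ACSA, at which visits and from whom, including placebo subjects from each contributing study.

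- **If collection continues, or data exist in all arms:** give both scales at the same visits in every arm, under a form name that does not mention amphetamine, and specify an AMPH-versus-PBO comparison for each.
- **If only AMPH-group data exist:** report both scales as descriptive and uncontrolled, say how the blind was kept, and do not use them for the Go safety condition.

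The first course costs a few minutes at existing visits and some SAP wording. The second costs wording and a weaker safety statement on movement and cessation symptoms.

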## Recruitment and Retention Plan

We anticipate that over the course of this study we will consent 69 SZ individuals for screening, from whom we will advance 54 individuals to in-laboratory baseline testing and randomization into two arms with n=27 per arm. After study attrition, we conservatively expect that 36 individuals will complete 30 hours of TCT and longitudinal (12 week post-TCT) testing, and that attrition will be roughly balanced to arrive completed samples of n=18 per study arm.

Example of CONSORT Diagram of proposed R33 study

\* Conservative estimate of final n=18/arm for Aim 2 analyses

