## **Adverse Events**

**Definition of Adverse Events (AEs):** An AE is defined as any untoward medical occurrence in a patient or clinical investigation subject administered a pharmaceutical product and which does not necessarily have to have a causal relationship with this treatment. An AE can therefore be any unfavorable and unintended sign (including an abnormal laboratory finding), symptom, or disease temporally associated with the use of a medicinal product, whether or not considered related to the medicinal product.

**Causal relationship of AEs:** Medical judgment will be used to determine the relationship, considering all relevant factors, including pattern of reaction, temporal relationship, confounding factors such as concomitant medication, concomitant diseases and relevant history, and reported as such to the DSMB.

**Vital signs** (measurements of systolic/diastolic blood pressure and pulse rate as outlined below) will be recorded at each study visit and at specific time points after AMPH/PBO ingestion. BP is measured using a brachial cuff on the non-dominant arm; pulse is measured manually for 30 seconds and multiplied by 2.

**Assessment of suicidality:** Suicidality will be monitored closely during the study period. Suicidal thoughts and behavior will be assessed by Columbia-Suicide Severity Rating Scale (C-SSRS). The C-SSRS is a questionnaire assessing both suicidal behavior and suicidal ideation. It consists of five questions related to suicidal behavior and five questions related to suicidal ideation, evaluated as either present or not. The C-SSRS will be administered by qualified clinicians and will be assessed at the screening visit with the aim to exclude patients with active moderate or severe symptomatology prior to the Screen Visit, or recent (or current) suicidal or suicide attempt according to the C-SSRS (baseline/screening version). Subsequently, the C-SSRS "since last visit" assessment will be performed at each visit as shown in the study Schematic. If there is a positive response of suicide attempt or suicidal ideation by the patient during the administration of the C-SSRS during the treatment period, a study MD will immediately interview the patient during the visit and determine if the patient will be discontinued from the trial and appropriate actions for the patient's safety have to be initiated. For assessment of the C-SSRS paper forms will be used and results will be transcribed into the DSMB report.

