Clinical, neurocognitive and functional outcome scores were treated as continuous variables and analyzed in three ways. First, they were submitted to linear mixed-effects (LME) models⁵⁹ for both between-group (interaction model: TCT+AMPH vs. TCT+PBO) and within-group (time model: baseline vs. P30, all groups) analyses. LME analyses included data from all randomized subjects (including those who did not complete 30 AT sessions) and modeled random intercepts to account for within-subject dependencies. Second, because sample sizes fell well below target levels, to test the hypothesis that active drugs would augment the impact of a 30-session course of TCT, the effect size (Cohen's d) of the change from baseline to P30 (“difference score”) was calculated for both between-group (TCT+AMPH vs. AT+PBO) and within-group (baseline vs. P30, all groups) comparisons. Between-group effect sizes were calculated as:

$$d = [(drug score T_1 - drug score P30) - (PBO score T_1 - PBO score P30)] / SD_{wav}$$

where SD_{wav} is the weighted average standard deviation. Within-group effect sizes were calculated as:

$$d = (score at T_1 - score at P30) / SD_{av}$$

where SD_{av} is the average of the standard deviations of the T_1 and P30 measures^{60,61}.

Third, to disentangle the salutary contributions of TCT alone vs. TCT+active drug to within-subject effect sizes, a “threshold” for positive active drug effects was set at “*d=0.4 above PBO values*”:

$$d(\text{active drug}) \geq d(\text{PBO}) + 0.4.$$

Because clinical gains from TCT+PBO were expected to be approximately $d=0.4$, this added threshold of “ $d=0.4$ above PBO” for drug-enhanced TCT meant that an estimated combined large effect size (at least $d=0.8$) would be required for a drug effect to be viewed as meaningful. Outcomes using thresholds from $d=0.2$ to $d=0.6$ were reported.

The use of effect size comparisons in addition to p-values is common in clinical trials research as a way to measure effects independent of sample size. It is particularly useful when, as in the current study, sample sizes fall below targets identified based on traditional power analyses. Effect size “thresholds” have been used by others to argue that TCT neurocognitive benefits exceed levels produced via PBO or practice effects (generally $d \approx 0.18$).

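### AIMS and the amphetamine cessation scale appear to be assigned to repeated-measures ANOVA, which drops patients with a missing visit; the plan's own mixed model would keep them

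*SAP*

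**What the plan says.** The last part of the SAP (Project Modification: Statistical Analysis Plan) lists indirect indicators of clinical impact: attrition, C-SSRS responses, treatment satisfaction and adverse events. It adds that AMPH-arm patients were assessed with AIMS and the AMPH Cessation Symptom Assessment. On method it says only: "Analyses included non-parametric (Chi-Square) and parametric (rmANOVA) tests". It does not say which test goes with which measure, which visits enter, who is analysed, or how missing visits are handled.

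For the outcome measures the same section is explicit: "LME analyses included data from all randomized subjects", including patients who did not finish the 30 sessions. Its outcome list has three primary and five secondary measures. AIMS and the cessation scale are not on it.

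The protocol treats the two scales differently. Under Symptoms (Specific Procedures) and in the outcome table of section 4.3, both are listed with the secondary clinical measures. Data Analysis specifies mixed models with full-information likelihood and every case included. General Clinical Monitoring says that data from non-completers go into linear mixed models.

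On attrition, the Recruitment and Retention Plan states "we will advance 54 individuals to in-laboratory baseline testing and randomization into two arms with n=27 per arm" and "we conservatively expect that 36 individuals will complete 30 hours of TCT and longitudinal (12 week post-TCT) testing".

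**The concern.** AIMS and the cessation scale are where abnormal movements and the effects of stopping amphetamine are measured as graded scores. A complete-case method leaves out anyone who misses a visit that enters the model. If patients who worsen are more likely to stop, those who remain are the better tolerators, and the mean change on the scale is too small. The SAP itself raises dropout related to the missing outcome as a concern (Procedures for Alternative or Unexpected Results). The protocol lists adverse effects of amphetamine on psychosis, akathisia or other symptoms as one possible reason for a failed result.

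For the cessation scale there is a further awkwardness: a patient who stops early has in fact experienced cessation, yet could be left out of the analysis of it.

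The remedy is already in the plan. The outcome scales have a mixed model that uses partial records, and the modification gives no reason for treating these two scales otherwise.

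**Working it through.** **Step 1. Which measures can repeated-measures ANOVA refer to?**

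| Measure in the SAP paragraph | Data type | Source | Natural test |
|---|---|---|---|
| Attrition | count | by definition | chi-square |
| Adverse events | count | Protocol, Adverse Events | chi-square |
| C-SSRS | items "evaluated as either present or not" | Protocol, Adverse Events | chi-square |
| Treatment satisfaction | rated once, after session 30 | Protocol, Function | no repeated measure |
| AIMS | scale score | Protocol, Symptoms | repeated-measures ANOVA |
| AMPH Cessation Symptom Assessment | scale score | Protocol, Symptoms | repeated-measures ANOVA |

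Only the last two remain. This is an inference from data types; the SAP does not state it.

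**Step 2. Does the mixed model cover them?** Primary outcomes: PANSS total, MCCB composite, WHODAS (3). Secondary: PANSS positive, PANSS negative, PHQ-9, YMRS, PSYRATS hallucinations (5). The total is 3 + 5 = 8, and neither scale is among them.

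**Step 3. How many patients could be lost?** From the Recruitment and Retention Plan, (54 − 36)/54 = 18/54 = 33.3%, or 9 of 27 per arm. This applies to the original 1:1 two-arm design and counts completion of the 12-week follow-up as well as training. The modified three-group design has no corresponding figure.

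**Step 4. What does that do to the estimate?** The documents give no variance, schedule or dropout model for either scale, so every input here is an assumption. One arm is measured at four visits, t = 0, 1/3, 2/3, 1:

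score = b + (0.5 + s)·t + e, with Var(b) = 0.6, SD(s) = 0.5, Var(e) = 0.4.

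The baseline SD is √(0.6 + 0.4) = 1, the baseline intraclass correlation is 0.6, and the true rise by the last visit is 0.5 SD. The log-odds of stopping before the next visit are a + k × (last observed change from baseline), with a tuned so that about one third stop. Completers' mean change is what a classical repeated-measures ANOVA estimates. The mixed model has visit as a factor. Two separate simulations gave:

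| k per SD | Completers | Mixed model, random intercept | Mixed model, random slope |
|---|---|---|---|
| 0 | 0.48 | 0.48 | not run |
| 1 | 0.37 and 0.38 | 0.49 and 0.48 | 0.52 |
| 1.5 | 0.30 | 0.47 | 0.51 |
| 2 | 0.25 and 0.27 | 0.42 and 0.45 | 0.45 |

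Where two values are shown, each comes from one simulation; differences of a few hundredths are simulation noise. Share of the true rise hidden among completers: (0.50 − 0.38)/0.50 = 24% at the low end and (0.50 − 0.25)/0.50 = 50% at the high end. With k = 0 the two methods agree, and the cost is precision only.

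**The case against.** A reader might infer that patients who stop early disappear from the safety analysis as a whole. The documents do not support that:

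- The protocol records any deterioration during the study as an adverse event.
- Adverse events, attrition and C-SSRS need no complete set of visits.
- PANSS, PHQ-9, YMRS and PSYRATS are in mixed models on all randomised patients.
- The SAP compares drop-out between arms.
- The safety element of the Go rule concerns adverse effects relative to placebo and does not name AIMS.

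At most two scales are affected.

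It is also fair to say that listwise loss is not a stated rule. The SAP allows multiple imputation or full-information likelihood where appropriate, and exiting patients are followed clinically to post-TCT week 12. An ANOVA on two visits, or on imputed data, would lose fewer patients or none. That stands as a reason to call the loss the default consequence of the named method. It does not close the gap. The modified section does not tie imputation to these scales, full-information likelihood is not part of classical repeated-measures ANOVA, and clinical follow-up is not said to include these scales. A later off-drug value would not replace an on-treatment one in any case.

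The simulation is open to the objection that neither scale has a stated visit schedule and that a steady rise on treatment does not describe a cessation scale. That stands: the figures illustrate a scale of the AIMS kind and are not estimates for this trial. Nor do the documents say that patients stop because of side effects.

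Finally, the SAP mentions these scales for the AMPH arm only. A mixed model corrects the within-arm change but supplies no placebo contrast.

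**Conclusion.** The point holds for AIMS and the AMPH Cessation Symptom Assessment only. The SAP's wording leaves these two scales with a method that, by default, omits early stoppers, while the protocol and the SAP's own outcome analyses use mixed models on partial records.

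The conclusion rests on the elimination in step 1 and on a classical, unimputed ANOVA across all visits. The one-third loss is the original design's expectation and cannot be carried over to the modified design. The size of any bias depends on how strongly stopping follows the score: about a quarter to a half of a 0.5 SD worsening under the assumed values, and none if the two are unrelated. The mixed model comes much closer but is not perfect; with the strongest dependence it gave 0.42 to 0.45.

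The change is worth making because it is specific and nearly free. It does not call the adverse-event comparisons into question.

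**What to change.** In the SAP paragraph on indirect indicators, name the test for each measure. For AIMS and the cessation scale, replace repeated-measures ANOVA with the linear mixed model already specified for the outcomes: visit as a factor, all randomised patients given the scale, all available visits. List the visits used. Beside the model, report the last on-treatment value of patients who stopped early, so that the reader can see whether they differed from those who stayed.

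The cost is a few lines of SAP wording and a rerun of existing code. No new data are needed.
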